2.3 Study Hypotheses

- (1) ^{177}Lu -OPS201 will be sufficiently safe to permit further clinical investigation when administered in previously treated subjects with unresectable GEP NETs, lung NETs and malignant, unresectable pheochromocytoma or paraganglioma.
- (2) Increase of peptide mass doses leads to improved tumour to background ratio for ^{177}Lu -OPS201 administration, with a possible positive impact on the safety profile with an increasing tumour to bone marrow ratio.

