3.1.3 Justification for Part B Design

In animal experiments, no saturation of the sstr2 was observed when higher peptide mass doses were administered in a xenograft mouse model.[39] Nevertheless, the effect of the increasing peptide mass dose and the peptide mass at which lesion receptor saturation occurs in humans is unknown. The extrapolation from animal experiments may be limited by the fact that, in these

xenografts, receptor density was relatively high in comparison to normal distribution of receptors in the mouse.

Receptor saturation by the peptide is predicated on:

- (a) the number of receptors in nontumoural tissue (physiological expression) and
- (b) tumour burden and related sstr2 density (total receptor burden).

Regardless of tumour type, the higher the receptor burden the more peptide maybe required before saturation occurs. It is therefore important that the peptide masses being studied in this protocol are evaluated for sstr2 saturation. Hence Cohorts 3 and 6 will evaluate the peptide mass and specifically if receptor saturation has occurred, starting with 300 µg for Cycle 1, then increasing to 700 µg and 1300 µg respectively for Cycle 2 before repeating the 300 µg dosing for Cycle 3 (see [Figure 13](#)). Thus, the tumour-to-background dose ratio, and the tumour-to-bone-marrow dose ratio, using imaging dosimetry, can be evaluated in the same subjects. In these cohorts, administering 4.5 GBq/cycle, which was shown to be tolerated in Part A of the study, will allow comparison of intra-subject variability of the uptake due only to the peptide mass. It also allows Cohort 3 to start in parallel to Cohort 1 which is the next logical increase in dosing at 300 µg (6 GBq per cycle) following Part A.

The other cohorts in Part B will be initiated in a staggered manner after gaining experience with previous cohorts, thereby allowing safer investigation at higher radioactivity and/or higher peptide mass dose. If tumour sstr2 saturation is observed, then the lower peptide dose will be confirmed. Therefore, Cohorts 7 and 8 will be cancelled if the peptide saturation is seen in Cohorts 3 and/or 6. Similarly, Cohort 2 may be cancelled if a peptide mass dose range of 700 µg to 1300 µg is found to be optimal.

Subject numbers

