1.3.1.2 Study drugs administered

The study will be performed in two parts.

Part A (15 subjects)

Initially, six subjects will be treated. Each subject will receive three cycles of 4.5 GBq (target radioactivity $4.5 \text{ GBq} \pm 10\%$) ^{177}Lu -OPS201 (target dose $300 \pm 50 \mu\text{g}$), every 8 weeks (+2 weeks or up to +4 weeks in case of AEs which have not adequately recovered). An SRC meeting will be held before exposing the remaining nine subjects to the entire number of planned administrations.

Part B (up to 40 subjects)

The following table provides the specific radioactivity and peptide mass dose for each cohort in Part B.

Table 1 Radioactivity and Peptide Mass Dose in Each Cohort and Cycle – Part B

Cohorts	Planned dose escalation			
	Nominal OPS201 dose per cycle (µg)	OPS201 range per cycle (µg)[a]	Nominal radioactivity and range (GBq)	Cumulative radioactivity (3 cycles, GBq)
1	300	[250 to 350]	6.0±10%	18.0
2[b]	300	[250 to 350]	7.4±10%	22.2
3	300 (Cycle 1) 700 (Cycle 2) 300 (Cycle 3) 300 (Cycle 4 and 5)[c]	[250 to 350] [550 to 850] [250 to 350] [250 to 350]	4.5±10%	13.5
4	700	[550 to 850]	6.0±10%	18.0
5	700	[550 to 850]	7.4±10%	22.2
6	300 (Cycle 1) 1300 (Cycle 2) 300 (Cycle 3) 300 (Cycle 4 and 5)[c]	[250 to 350] [1100 to 1500] [250 to 350] [250 to 350]	4.5±10%	13.5
7[b]	1300	[1100 to 1500]	6.0±10%	18.0
8[b]	1300	[1100 to 1500]	7.4±10%	22.2

DOTA=tetraxetan; GBq=gigaBecquerel; IRPP=investigational radiopharmaceutical product; OP201=somatostatin analogue peptide JR11 coupled to DOTA.

a IRPP will be provided either through local or centralised manufacturing. OPS201 ranges include the ranges validated for local IRPP manufacturing in radiopharmacy of selected centres and the general validated range for centralised IRPP manufacturing (i.e. nominal OPS201 dose±15%).

b optional.

c For additional cycles, if any

At each PRRT cycle, the study medication will be administered after the conduct of a safety examination of the subject. The IRPP (20 mL of ¹⁷⁷Lu-OPS201) will be administered once per cycle by an i.v. infusion at a rate of 10 mL/h over 120 minutes. Infusion rate modification (up or down) would be under the investigator’s judgement and may be temporarily halted or even further slowed down if the subject does not tolerate the IRPP infusion. The overall infusion duration should not exceed 4 hours.

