Cumulatively excreted radioactivity in urine (unit: MBq) will be listed by study part, cohort (part B only), radioactivity level adapted or not (part B only), subject, cycle and time period.

Descriptive statistics, including geometric mean and geometric Coefficient of Variation (CV), will be presented by study part, cohort (part B only), cycle and time period on the ITT Set.

(b) Radiation Dosimetry

- Organs receiving the highest absorbed dose (unit: Gy).

All organs with their absorbed dose will be listed by study part, cohort (part B only), radioactivity level adapted or not (part B only), cycle, organ and subject on the ITT- DAS, and highest dose will be flagged.

- Specific absorbed dose to the lesions selected for the dosimetry evaluation (unit: Gy/GBq).

Specific absorbed dose to the lesions selected for the dosimetry evaluation will be listed by study part, cohort (part B only), radioactivity level adapted or not (part B only), subject, cycle and lesion number. Descriptive statistics, including geometric mean and geometric Coefficient of Variation (CV), will be presented by study part, cohort (part B only), cycle and lesion location on the ITT- DAS and PP-DAS. Descriptive statistics will also be presented on combined lesions on the PP-DAS population.

- Specific absorbed dose per organ (unit: Gy/GBq).

Specific absorbed dose per organ will be listed by study part, cohort (part B only), radioactivity level adapted or not (part B only), subject, cycle and organ. Descriptive statistics, including geometric mean and geometric Coefficient of Variation (CV), will be presented by study part, cohort (part B only), cycle and organ on the ITT- DAS and PP-DAS.

- Ratio of Specific absorbed dose per organ and lesion.

Ratio of specific absorbed dose at visits (e.g. visit 2 relative to visit 1, visit 3 relative to visit 1, visit 2 relative to visit 3, etc..) will be calculated per organ and per lesion and by study part (Part A and B), and by each cohort (applies to part B only), radioactivity level adapted or not (applies to part B only), subject, cycle and organ. Descriptive statistics, including geometric mean and geometric Coefficient of Variation (CV), will be presented by study part, cohort (part B only), cycle and organ on the PP-DAS.

Boxplots representing the ratio of specific absorbed doses between visits by organ and lesion will be produced.

- Tumour average/kidney ratio

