Ratio of tumour/average kidney ratio between visits by organ or combined lesions will be calculated per lesion and by study part (Part A and B), and by each cohort (applies to part B only), radioactivity level adapted or not (applies to part B only), subject and cycle.

Descriptive statistics, including geometric mean and geometric Coefficient of Variation (CV), will be presented by study part, cohort (part B only), cycle and organ on the PP-DAS.

- Cumulative absorbed organ doses (unit: Gy)

Cumulative absorbed organ doses will be listed by study part, cohort (part B only), radioactivity level adapted or not (part B only), organ and subject.

Descriptive statistics, including geometric mean and geometric Coefficient of Variation (CV), will be presented by study part, cohort (part B only) and organ on the ITT- DAS and PP-DAS.

CCI

(d) OPS201 Pharmacokinetics (Part B only)

Analysis of PK data by non-compartmental approach will be documented in a separate analysis plan. A listing of PK sampling time deviation from the scheduled time will be provided on OPS201 PK population. A listing of individual OPS201 concentrations per time point will be provided on OPS201 PK population.

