3.2.17 Interim analysis

1st Interim analysis

A first interim analysis will be conducted at the cut-off date of 27 September 2019 to inform the design of the chemotherapy combination study which has been added to the investigational plan.

The tables, listings and figures that will be produced for this analysis are flagged “*” in Section 7.2 – List of TFLs.

2nd Interim analysis

A second interim analysis of Part B data will be conducted at the EOCT/EOAC/EW (whichever occurs last) after completion of Cohorts 3 and 6. This will provide confirmation of the peptide dose to allow future studies to be developed. It will also confirm if Cohorts 2 or 7 and 8 will be initiated.

3rd Interim analysis

A third interim analysis, including all dosimetry, safety and efficacy data, will be performed after the EOCT/EOAC/EW (whichever occurs last) when the two study parts are completed.

The interim analyses may be combined based on the overall study status and subject accrual. The final analysis will be performed at the end of the 2-year long-term follow-up period.

Other analyses

In addition, dosimetry evaluation will be performed on an ongoing basis. After the first six subjects included have completed the study Part A (EOCT or Early Withdrawal Visit) an SRC meeting will be held before exposing the remaining subjects to the entire number of planned administrations. Safety data obtained until 8 weeks after the last administration of the 6th subject will be evaluated during this SRC. Prior to Part B, the SRC will review the safety and dosimetry data of the first six subjects included in Part A.

For Part B, a DRB meeting will be held to review the safety and radiation exposure data and decide whether to proceed with the enrolment of the next cohort dose level and the cumulative radioactivity within a cohort. Each dose escalation (both peptide and radioactivity) will be carefully evaluated by a DRB.

In addition, the SRC/DRB can be convened at any time during the trial to discuss potential safety issues. The data set to be reviewed by the SRC/DRB is specified in a specific charter.

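### Cohorts 3 and 6: the visible SAP reports visit-to-visit dose ratios separately, names no combined drift-adjusted peptide-mass estimate with an interval, and shows no tumour-to-bone-marrow ratio

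*SAP*

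**What the plan says.** **Design.** Protocol 3.1.3 and the Part B dosing tables (Protocol Table 11, SAP Table 1) give Cohort 3 the sequence 300-700-300 µg and Cohort 6 the sequence 300-1300-300 µg, all at 4.5 GBq per cycle. Protocol 1.7 describes this as a test-retest around the second cycle. Holding activity at 4.5 GBq, the protocol says, "will allow comparison of intra-subject variability of the uptake due only to the peptide mass".

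**Target quantities.** Hypothesis 2 (Protocol 2.3) is that more peptide improves the tumour-to-background ratio, "with a possible positive impact on the safety profile with an increasing tumour to bone marrow ratio". Protocol 3.1.3 says that the tumour-to-background and the tumour-to-bone-marrow dose ratios can both be evaluated in the same subjects.

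**Planned analysis.** SAP 3.2.2(b) computes ratios of specific absorbed dose between visits, per organ and per lesion, by study part and cohort: "visit 2 relative to visit 1, visit 3 relative to visit 1, visit 2 relative to visit 3". These are given as examples and the list is left open. They are summarised on the PP-DAS with geometric mean and geometric CV, and shown as boxplots. The one tumour-to-organ comparison in the visible text is the next item: "Ratio of tumour/average kidney ratio between visits by organ or combined lesions".

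**Use.** Of the second interim analysis, SAP 3.2.17 says: "This will provide confirmation of the peptide dose to allow future studies to be developed". The same analysis is to confirm whether Cohorts 2, 7 and 8 open. In SAP Table 9, DRB-D and DRB-E turn partly on lesion receptor saturation in Cycle 2 of Cohort 6, and DRB-F on mass-dose modelling.

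**The concern.** Every cycle is a therapeutic administration, and Protocol 3.1.3 itself makes saturation depend on tumour burden and receptor density. Treatment is meant to change the first and could change the second. Lesion dose per GBq may therefore move from cycle to cycle with no effect of peptide mass, and any ratio with visit 2 on top carries that movement with the peptide effect.

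The return to 300 µg in Cycle 3 is what allows the two to be separated, but the visible plan stops short of doing it. It does not say which ratio answers the peptide question, how the ratios combine, or how precise the answer is. If V2/V1 and V2/V3 disagree, the choice between them would be made after seeing them. At stake are the peptide mass carried into later studies and the opening of Cohorts 2, 7 and 8.

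Separately, bone marrow is where the protocol places the hoped-for safety gain, yet the visible SAP pairs the tumour with kidney only.

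**Working it through.** **1. The plan's own figure.** Inputs (Protocol 11.2, SAP 1.3.7): n = 8, SD of the paired difference 30%, two-sided alpha 0.05, 80% power for a 2-fold and 99% for a 3-fold change. Formula: power = Φ(√n × δ/SD − 1.960). Taking δ and SD in log10 units, with SD = 0.30:
- 2-fold: √8 × 0.301/0.30 = 2.838; 2.838 − 1.960 = 0.878; power 81.0%.
- 3-fold: √8 × 0.477/0.30 = 4.498; 4.498 − 1.960 = 2.538; power 99.4%.

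The figures reproduce under that reading, which the documents do not state. An SD of 0.30 on the natural-log, log2 or raw scale gives about 100% for both. A paired t-test on the log10 reading gives 68.4% and 96.9%. The calculation concerns a single pair of cycles, and neither document says which pair.

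**2. Drift.** V1, V2 and V3 are a subject's Gy/GBq at visits 1 to 3, p is the true peptide ratio, and c is a constant multiplicative change per cycle. Then V1 = 1, V2 = p·c, V3 = c², so V2/V1 = p·c, V2/V3 = p/c, V3/V1 = c² and V2/√(V1×V3) = p. The documents give no value for c, so a range is assumed, with p = 1:

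| Fall per cycle | V2/V1 | V2/V3 | V3/V1 | V2/√(V1×V3) |
|---|---|---|---|---|
| 10% (c = 0.9) | 0.90 | 1.11 | 0.81 | 1.00 |
| 20% (c = 0.8) | 0.80 | 1.25 | 0.64 | 1.00 |
| 30% (c = 0.7) | 0.70 | 1.43 | 0.49 | 1.00 |

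Read alone, V2/V1 would look like saturation and V2/V3 like a gain.

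**3. What the planned ratios already contain.** √[(V2/V1)×(V2/V3)] = V2/√(V1×V3), so the adjusted point estimate follows from the planned geometric means if the same subjects supply all three cycles. Its log-scale variance is then also recoverable: [2Var(V2/V1) + 2Var(V2/V3) − Var(V3/V1)]/4.

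**4. Precision.** With log-scale variance σ² per cycle and independent cycle errors (equal correlations give the same comparison), a single pair has variance 2σ² and the contrast (1 + ¼ + ¼)σ² = 1.5σ². The SE ratio is √(1.5/2) = 0.866, or 13% smaller, equivalent to 8/0.75 = 10.7 subjects. On the scale of step 1 the SD becomes 0.30 × 0.866 = 0.260, and power for a 2-fold change at n = 8 becomes 90.6% (z) or 80.2% (paired t).

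**5. Limits.** With six complete triples the contrast has variance 1.5σ²/6 = 0.25σ², the same as 2σ²/8 for a pair in all eight, so the gain is gone. If drift is not log-linear, say a factor of 0.7 and then 0.9 with p = 1, then V1 = 1, V2 = 0.70 and V3 = 0.63. The contrast is 0.70/√0.63 = 0.88, against V2/V1 = 0.70 and V2/V3 = 1.11.

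**6. Marrow inputs.** Protocol 11.4.6 has bone marrow and kidney absorbed doses evaluated before each next cycle, and SAP 3.2.2(b) lists specific absorbed dose by subject, cycle and organ. A marrow ratio would therefore be a derived variable, not a new measurement.

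**The case against.** Much of the case on the other side stands.

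- **Drift is not ignored.** A reader might infer that the SAP has no check on cycle order. It has: V3/V1 compares two 300 µg cycles and would show the drift plainly (0.81, 0.64 and 0.49 in the table). The list of ratios is open. Part A, at 300 µg and 4.5 GBq throughout, supplies the same ratios at constant peptide mass, though in other subjects and with SPECT/CT at 24 hours only (Protocol 9.2.2).
- **Information is not lost.** On complete data the contrast can be recovered from planned outputs. What is missing is a named estimate and its interval. Recovery is not assured if subjects lack Cycle 3, because the pairwise summaries then rest on different subjects. Protocol 3.1.2 counts some subjects with fewer than three cycles as completed.
- **The protocol does not deny cycle effects.** Its remark on uptake due to peptide mass alone gives the reason for holding activity constant and makes no claim about order.
- **Redaction.** SAP 3.1.4, item (c) of SAP 3.2.2 and the text of 3.1.7.4 Modelling are blacked out or not visible, and the DRB matrix refers to modelling. One cannot say that a tumour-to-bone-marrow ratio or a combined estimate is absent from the whole SAP.
- **Hypothesis 2** names tumour-to-background first; bone marrow is its safety part.
- **Early DRB decisions.** A reader might infer that DRB-A and DRB-B act on confounded ratios. Their visible criteria use DLT rates only. No text says that V2/V1 alone would be read as saturation.
- **Descriptive study.** SAP 3.1.9 plans no formal test. An estimate with an interval needs none, and the SAP already gives 95% CIs for Karnofsky score, response rate and quality of life. Protocol 11.4 allows intervals as appropriate but does not attach one to these ratios.

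**Conclusion.** The point holds as a gap in specification in the visible text. The sequence was chosen to isolate peptide mass, but no single within-subject estimate using all three cycles is named, and no interval is given. Under an assumed constant fall of 10% to 30% per cycle and no peptide effect, the two visit 2 ratios differ from 1 in opposite directions (0.90 to 0.70 against 1.11 to 1.43), while the combined contrast is 1.00. On complete triples with equal variances and correlations it also has a 13% smaller SE. The size of any real drift is unknown.

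The marrow part is narrower: the protocol says the ratio can be evaluated, and the visible SAP shows only kidney. The documents do not support concluding that the SAP overlooks drift, or that the marrow ratio will go unestimated.

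This is an inexpensive improvement that bears on a decision the trial intends to make.

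**What to change.** In SAP 3.2.2(b), for Cohorts 3 and 6:

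1. Name the within-subject ratio V2/√(V1×V3), with geometric mean and 95% CI, as the main peptide-mass contrast for Gy/GBq in lesions, kidney and bone marrow, and for tumour/kidney and tumour/bone marrow. Form it once per subject, so that the interval counts subjects and not lesions.
2. Show the planned V3/V1 beside it, with the Part A ratios, as the drift check. Keep V2/V1 and V2/V3 as supportive.
3. Use the contrast at the second interim analysis and where the DRB reviews Cycle 3 data (DRB-D, DRB-E and DRB-F).
4. If a blacked-out section or the modelling plan already defines this, cite it instead.

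No change is needed for DRB-A or DRB-B.

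Cost: SAP wording and a few variables derived from absorbed doses already computed. Only log-linear drift is removed. Subjects without Cycle 3 dosimetry contribute only to the supportive ratios, so the number of complete triples should be reported with the estimate.

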3.2.3 Efficacy

All efficacy data will be included in the data listings and summary tables based on the ITT and PP sets. Summary tables will be presented by study part, cohort (part B only), overall part B and overall.

Tumour response will be evaluated by an independent central review and by the site investigator.. Response and progression will be evaluated using the revised RECIST guideline v1.1 and a modified RECIST (will be analysed for both Part A and B. The efficacy endpoint in the protocol only focus on Part B patients) guideline. Only subjects with measurable disease at baseline, who have received at least one cycle of therapy, and have had their disease re-evaluated will be considered evaluable for response.

Investigator assessment using RECISIT (V1.1) will be the primary assessment whereas central RECIST (V1.1) and mRECISIT (part B only) will be sensitivity analysis.

a) Overall Response, Best Overall Response and Overall Response Rate

Overall response at each visit will be tabulated and listed, as well as Best Overall response according to RECIST/CCI. Subjects with concurrent use of somatostatin analogues will be flagged in the listing.

For analysis of the ORR, summary tables will be generated, presenting the number and proportion of responders by study part, cohort (part B only) and overall on the ITT and PP sets, together with two-sided 95% Clopper-Pearson CIs. Subjects with no tumour assessment after the start of study treatment will be excluded from the analysis.

The same analysis might be repeated in the subsets of subjects with and without concurrent use of somatostatin analogues, if deemed relevant by the Sponsor.

The following SAS® code will be used for tables that need exact 95% Clopper-Pearson CIs:

```
PROC FREQ DATA=dset NOPRINT;  
    BY by var; (optional)  
    TABLES var1 /binomial (exact);  
    OUTPUT OUT=outname;  
RUN;
```

b) Disease control rate (DCR)

The number and proportion of subjects with disease control at end of either EOCT/EOAC (if independent central read) or end of long-term follow-up (if investigator) will be presented per study part, cohort (part B only) and overall on the ITT and PP sets, together with two-sided 95% Clopper-Pearson CIs. Subjects with no tumour assessment after the start of study treatment will be excluded from the analysis. The DCR will be based on the best overall response over all timepoints for independent central review and investigator assessment.

For investigator data, the DCR rate at selected timepoints (Month 12, 18, 24) will also be generated. For DCR at month 12 (resp. 18 and 24 month), the analysis will include all patients who are on study at month 12 (resp. 18 and 24 month) defined as 365 days – 28 days (resp. 545 - 28 and 730- 28) relative to the first dose or patients who had early PD or death prior to that time. The best overall response category of CR, PR or SD in patients who have not had an early PD or death up to the timepoint will represent the subjects with disease control

c) Sum of Diameters

Descriptive statistics and 95% CIs of the mean for percentage change from baseline will be calculated by study part, cohort (part B only) and overall at Follow-up Visit 2, EOCT, EOAC (if any) and Long-Term Follow-up visits on the ITT and PP sets. The length of the longest diameter will also be presented.

Percent change and best percent change in sum of diameters will be listed.

Percent change of sum of diameters according to RECIST ^{CCI} will also be plotted by study part and cohort (part B only) at Visit 2, EOCT Visit, EOAC Visit (if any) and Long-Term follow up visits 1 and 2 on the ITT set.

Waterfall plots presenting best overall response (RECIST ^{CCI}) versus best percent change from baseline of sum of target lesion diameters over the whole study will be performed on the ITT set.

d) Progression Free Survival (PFS) from independent central review and from investigator assessment

PFS, defined as the time from first study drug administration to progression or death which ever occur first, will be analysed.

Disease progression will be assessed by tumour response evaluation according to RECIST v1.1/ ^{CCI}, measured using the same imaging technique (ceCT scan or MRI) for each subject throughout the study.

Event dates are assigned to:

- The first time when progressive disease was noted, or
- Date of death.

In case of progressive disease followed by death, the first event will be considered in the analysis. The date of progression will be recorded as the date of the last radiographic evaluation included in the series for that assessment.

Censoring dates are defined in subjects with no progressive disease or death before end of study or withdrawal. In these subjects, the censoring date is defined as the last date on which overall

RECIST status was evaluable. This is taken to be the date of the last radiological assessment at which the target lesions were evaluated (see Table 7).

Table 7 Censoring Rules for PFS

Reason for censoring	Rule
No screening evaluable[a] assessment	Date of first treatment administration
Two or more not evaluable (NE) consecutive assessments before progressive disease or death	Date of last evaluable disease assessment before the second NE assessment
No progressive disease	Date of last evaluable disease assessment
Treatment discontinuation for undocumented progression	Date of last evaluable disease assessment
Treatment discontinuation for toxicity or other reason	Date of last evaluable disease assessment
Initiation of medications or therapy not permitted during the study	Date of initiation of non-permitted medication or therapy

a An assessment is considered NE when no imaging/measurement is done at all at a particular time point, or only a subset of lesion measurements are made at the time point. The subject is considered NE at that time point.

For central reading assessments, patients will be censored at the timepoint of the last central assessment at or before EOCT/EOAC.

The PFS time will be calculated as the time from first administration of the study drug to either progressive disease or death as follows.

$$\text{PFS time (in months)} = [(\text{Date of event} - \text{date of first administration of study drug} + 1) / 30.4375]$$

Data will be analysed by study part, cohort (part B only) and overall part B on the ITT and PP sets. The distribution of PFS times will be estimated using the Kaplan Meier method for each study part, cohort (part B only) and overall Part B. The median PFS time will be presented with its associated 95% CI, together with the number and percentage of events, by study part, cohort (part B only) and overall. The results will also be presented graphically in Kaplan Meier plots.

Completely missing tumour data: when tumour assessment visits are completely missing, FDA Guidance “Clinical Trial Endpoints for the Approval of Cancer Drugs and Biologics” [4] states that "events occurring after two or more missed radiological assessments will be censored in the analysis at the last adequate assessment”.

This will be implemented as follows:

[figure not shown]
Progressive Diseases (PDs) occurring after two or more missed radiological assessments will be censored in the analysis at the last adequate* assessment before the missing assessments: If a subject has one missed radiological assessment before a PD, the PD will be analysed as an event (i.e. a PD is analysed as an event if the previous radiological assessment was performed within approximately the last 6 months).

Table 8 Event status for various scenarios with missing data

Scan Time	FU Visit 2	EOCT/EOAC / EW Visit	Long-term Follow-up Visits n	Long-term Follow-up Visits n +1	Event status
Scenario 1	missing	PD			Event at EOCT/EOAC/EW visit
Scenario 2	missing	missing	PD		Censored at Baseline
Scenario 3	missing	SD	PD		Event at Long-term Follow-up Visit n
Scenario 4	missing	missing	SD	PD	Event at Long-term Follow-up Visit n+1
Scenario 5	SD	SD	missing	PD	Event at Long-term Follow-up Visit n+1
Scenario 6	SD	missing	missing	PD	Censored at FU Visit 2

e) Dosing and dosimetry in conjunction with tumour burden

A figure depicting the following relationship displaying the Pearson’s correlation coefficient (and the associated 95% confidence interval):

- CCI
 -
- 

f) Quality of life

- EORTC QLQ C30 v3.0

For QLQ C30 global health status score, functional scales scores and symptom scales scores, descriptive statistics and 95% CIs of the mean will be presented for the raw data and for the changes from baseline during treatment, by study part, cohort (part B only) and overall at each visit (Visit 1, 2, 3, optional visits (if any) and EOCT/EOAC Visits) on the ITT and PP sets.

For the evaluation of the QLQ C30 scores values at baseline the EORTC QLQ C30 Reference Values manual (Ref. 12) or a more up to date reference will be used.

- EORTC QLQ – GI.NET21 (2006)

For GI.NET21 endocrine symptoms scale score, G.I. symptoms scale score, treatment related symptom scale score, social function scale score, disease related worries scale score, muscle /bone pain symptom item, sexual function item, information/communication function item and body Image item, descriptive statistics and 95% CIs of the mean will be presented for the raw data and for the changes from baseline during treatment, by study part, cohort (part B only) and overall at each visit (Visit 1, 2, 3 and EOCT Visit) on the ITT and PP sets.

g) Duration of Response (DoR)

DoR refers to the time when complete response (CR) or partial response (PR) is first observed until the time of progressed disease (PD) or death for the subjects whose best overall response is complete response (CR) or partial response (PR). If the subject did not have an event of PD or death, then DoR will be the time of last tumor assessment.

DoR will be listed.

Summaries of DoR will include summary statistics of duration, the number and the associated percentage of patients whose DOR is >3, >6, >9 and >12 months for Part A and Part B and overall (Part A and B). In case of sufficient responders, the median of DOR (calculated based on Kaplan-Meier) and 95% confidence interval of median time will also be summarized.

h) Tumour Volume (mL)

Tumour Volume (mL) is measured for each lesion at each scheduled visit by independent central review using RECIST (v1.1) and CCI. The sum of the tumour volume (mL) per visit will be computed and descriptive statistics of tumour volume, change in tumour volume and percentage change in tumour volume will be generated at each scheduled visit on the ITT and PP sets.

